8.3.2 Statistical analyses

Data from all participating study centers will be combined for analysis. The core study report will include patient data until the time point when the last patient has completed at least two cycles of treatment or discontinued the study.

In the case that patients continue to receive study drug past this time (in accordance with the protocol) an extension report will be prepared once these patients have completed the study, or have been discontinued.

An interim analysis for stage transition in the Phase 2a dose expansion portion will be performed when the specified number of patients required for Stage 1 had at least one post-baseline RANO assessment after having received at least 6 weeks of study treatment, but no later than after the completion of Cycle 12.

If the required number of responses has not been observed at the time of enrollment of the last patient in Stage 1, enrollment may be suspended, or the cohort may be terminated due to apparent futility. If the required number of responses is reached earlier, the interim analysis may be performed earlier, and stage transition may occur based on a joint decision taken by the Investigators and the Sponsor (see Section 3.1.3).

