8.1 Study variables

Primary study endpoints:

- Phase 1: Frequency and characteristics of BAL101553-related DLT, or other toxicities which are relevant for determination of the MTD.
- Phase 2a expansion portion (Simon's two-stage design): Best objective response according to RANO criteria.

Secondary endpoints:

- Overall safety endpoints:
 - Type and frequency of AE, SAEs, laboratory, echocardiogram and ECG abnormalities; abnormalities in vital signs, physical examination results, chest X-ray/CT; frequency and causes of study withdrawals and dose modifications.
- Efficacy endpoints:
 - Best objective response according to RECIST 1.1 in patients with solid tumors, based on the change from baseline in tumor measurements as measured in patients with measurable disease, and according to RANO criteria in patients with progressive or recurrent GBM or high-grade glioma (Phase 1 only).
 - Change from baseline in tumor markers (CA-125, PSA) in patients whose disease is characterized by these tumor markers utilizing Rustin criteria for ovarian cancer or PSA Working Group 2 criteria for prostate cancer.
 - Progression-free survival and OS.
- Pharmacokinetic assessments (BAL101553 and BAL27862):
 - C_{max}, T_{max}, AUC_{0-t}, AUC_{0-τ}, AUC_{0-last}, AUC_{0-∞}, t_{√2}, systemic clearance and volume of distribution.
 - Total 24 h urinary excretion of BAL101553 and BAL27862.
- Exploratory endpoints:
 - Change from baseline in biomarkers (including but not limited to numbers of CTCs, CECs, CEPs).

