8.3.3.2 Phase 2 dose expansion portion (Simon's two-stage design)

Simon's two-stage design will be used in Phase 2a. The null hypothesis that the true response rate is 14% will be tested against a one-sided alternative. In the first stage, 9 evaluable patients will be accrued. If there are 1 or fewer responses in these 9 patients, the study will be stopped. Otherwise, 10 additional evaluable patients will be accrued for a total of 19. The null hypothesis will be rejected if 6 or more responses are observed in 19 patients. This design yields a type I error rate of 3.7% and power of 81% when the true response rate is 40%.

For actual patient numbers see Section 3.3.

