3.3.3 Planned sample size

Phase 1 dose escalation portion

The accelerated 3+3 design applied in Phase 1 does not require sample size specification; the escalation is continued until the MAD (i.e., a dose with an unacceptable number of DLT) is observed. The expansion portion is exploratory; therefore, no statistical sample size justification has been applied.

The dose escalation portion of the study is completed. 26 patients with advanced or recurrent solid tumors and 28 patients with recurrent or progressive GBM or high-grade glioma were dosed. In each of the groups, 24 patients were evaluable for MTD assessment.

Phase 2 dose expansion portion (Simon's two-stage design)

Simon's two-stage design will be used in Phase 2a. The null hypothesis that the true response rate is 14% will be tested against a one-sided alternative. In the first stage, 9 evaluable patients will be accrued. If there are 1 or fewer responses in these 9 patients, the study will be stopped. Otherwise, 10 additional evaluable patients will be accrued for a total of 19. The null hypothesis will be rejected if 6 or more responses are observed in 19 patients. This design yields a type I error rate of 3.7% and power of 81% when the true response rate is 40%.

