3.4 Interim analyses

No interim analyses are planned for the phase 1 portion of the study. Upon completion of the phase 1 portion of the study, the Phase 1 data will be cleaned and data will be locked. Advanced or recurrent solid tumors and recurrent or progressive GBM or high-grade glioma will be analyzed separately.

The phase 2a parts will also be analyzed separately once data are cleaned and data locked.

An interim analysis for stage transition in the Phase 2a dose expansion portion will be performed when the specified number of patients required for Stage 1 had at least one post-baseline RANO assessment after having received at least 6 weeks of study treatment, but no later than after the completion of Cycle 12.

If the required number of responses has not been observed at the time of enrollment of the last patient in Stage 1, enrollment may be suspended, or the cohort may be terminated due to apparent futility. If the required number of responses is reached earlier, the interim analysis may be performed earlier, and stage transition may occur based on a joint decision taken by the Investigators and the Sponsor.

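### Neither the timing of the Stage 1 futility count nor the response window is fixed, so the stated 81% power is an upper bound

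*Protocol*

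**What the plan says.** **Endpoint.** Protocol 8.1 gives the Phase 2a primary endpoint as "Best objective response according to RANO criteria". No response window is stated there, in Protocol 8.3.2.5 or in SAP 6.2.1.

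**Design.** Protocol 8.3.3.2: "The null hypothesis that the true response rate is 14% will be tested against a one-sided alternative". Stage 1 takes nine evaluable patients, with this futility rule: "If there are 1 or fewer responses in these 9 patients, the study will be stopped". A trial that passes adds ten more, and 6 or more responses among all 19 reject the null. SAP 3.3.3 repeats the rule and adds: "This design yields a type I error rate of 3.7% and power of 81% when the true response rate is 40" per cent.

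**Timing of the look.** SAP 3.4 sets the trigger by patient count: "An interim analysis for stage transition in the Phase 2a dose expansion portion will be performed when the specified number of patients". The condition is that each of these Stage 1 patients has been assessed by RANO at least once after baseline. Protocol 8.3.2 sets the bounds as "after having received at least 6 weeks of study treatment, but no later than after the completion of Cycle 12". Twelve 28-day cycles are 48 weeks. The text does not say whose Cycle 12 is meant.

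**Follow-up.** Patients with stable disease may stay on drug (Protocol 5.6 and 4.4). MRI is due at the end of even-numbered cycles, about every 8 weeks (Protocol 3.1.3).

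**Data cut.** The core report takes data until the last patient has completed two cycles or discontinued; later data go to an extension report (Protocol 8.3.2, SAP 6). Neither document says which cut carries the primary test.

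**The concern.** The 3.7% and 81% come from a calculation in which a patient's response status is complete when it is counted, both at Stage 1 and at the end. The text does not secure this.

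Take a Stage 1 patient who is stable at the first scan and still on drug. If the look is taken then, the patient is a non-response. If the response appears at the Cycle 4 or Cycle 6 scan, it would have counted towards the 6 of 19, but the trial may already have stopped. There is no pending category, and the stop is worded as automatic.

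The exposure is to false futility. Stage 2 and the Surgical cohort both depend on passing Stage 1. At the assumed EB1-positive prevalence of 2–4%, each eligible patient takes 25–50 tissue screens (Protocol 1.5.2.2.2), so a stopped cohort would be slow to rebuild. The open timing also means the same nine patients could pass or fail depending on the date of the look.

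Two neighbouring matters are separate and not counted here: whether a response needs the 4-week confirmation before it counts, and the option to suspend or terminate when the last Stage 1 patient enrolls.

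**Working it through.** **Inputs from the documents** (Protocol 8.3.3.2): n1 = 9, stop at ≤ 1 response; n = 19, reject at ≥ 6; p0 = 0.14; p1 = 0.40.

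**Assumed, because the documents give neither:** k, the number of Stage 1 patients whose follow-up is immature at the look; and v, the share of eventual responses in those k patients that is visible at the look. Ranges: k = 3, 5, 9; v = 0.8, 0.7, 0.6. In the main table, late responses in a trial that continues are all counted in the final 19.

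**Step 1: the plan's own figures.**

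False stop at 40%: 0.6^9 + 9 × 0.4 × 0.6^8 = 0.0101 + 0.0605 = 0.0705.

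Power = Σ over x = 2..9 of P(Bin(9, 0.4) = x) × P(Bin(10, 0.4) ≥ 6 − x):

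- x = 2: 0.1612 × 0.6177 = 0.09960
- x = 3: 0.2508 × 0.8327 = 0.20886
- x = 4: 0.2508 × 0.9536 = 0.23920
- x = 5: 0.1672 × 0.9940 = 0.16620
- x ≥ 6: 0.09935

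Total 0.8132. The same sum at 0.14 gives 0.0371. Both stated figures reproduce.

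**Step 2: immature follow-up at the look.** Let A ~ Bin(9 − k, p) be responses in mature patients, and split the k immature patients into S visible responders (probability pv each), L later responders (p(1 − v)) and non-responders (1 − p). The trial continues if A + S ≥ 2 and succeeds if A + S + L plus the Stage 2 responses reach 6.

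False stop = P(A + S ≤ 1). Example, k = 3, v = 0.8, so pv = 0.32:

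- none visible: 0.6^6 × 0.68^3 = 0.0147
- one visible: 6 × 0.4 × 0.6^5 × 0.68^3 + 0.6^6 × 3 × 0.32 × 0.68^2 = 0.0587 + 0.0207 = 0.0794
- total: 0.0941

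Power = Σ over A + S ≥ 2 of P(A, S, L) × P(Bin(10, 0.4) ≥ 6 − A − S − L).

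| k immature | v | False stop at 40% | Power at 40% |
|---|---|---|---|
| 0 (design) | – | 7.1% | 81.3% |
| 3 | 0.8 / 0.7 / 0.6 | 9.4 / 10.7 / 12.2% | 79.8 / 78.9 / 77.9% |
| 5 | 0.8 / 0.7 / 0.6 | 11.3 / 14.1 / 17.2% | 78.5 / 76.5 / 74.1% |
| 9 (worst case) | 0.8 / 0.7 / 0.6 | 16.3 / 23.4 / 32.5% | 74.8 / 69.1 / 61.5% |

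Power falls by less than the false-stop probability rises, because some of the stopped trials would have missed 6 of 19 anyway. With k = 9, power passes below 80% once about 6% of eventual responses are not yet visible.

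**Step 3: type I error.** The same sums at p = 0.14 with k = 9 give 3.2 / 2.8 / 2.4%, below 3.7%. An immature look only adds chances to stop.

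**Step 4: the other end.** Hold Stage 1 fully mature and let the core-report cut leave the last 3 of the 19 patients with 80 / 70 / 60% of their responses visible (response probability 0.4v in those 3). Power is then 78.9 / 77.5 / 76.2%. So the final count is also exposed.

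**The case against.** The strongest reply is that the text already permits a mature look. One scan is a minimum, the look may wait until Cycle 12, and enrollment may be suspended meanwhile. With a mature Stage 1 count and complete follow-up of the final 19, power is 81.3% exactly. That stands. A reader might infer that 81% is simply not delivered, but the documents support only that it is not guaranteed: the loss depends on a date they leave open and on a response-time distribution they do not give.

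Accrual is the second reply. At 2–4% prevalence patients probably enter one by one, so the earliest will have had several scans before the ninth has one. No accrual rate is given, so this is inference, but it makes 3 to 5 immature patients more plausible than 9. The all-9 row is a worst case.

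Third, a reader might contrast a short window at the look with an unlimited one at the end. The documents do not establish that contrast, because the two-cycle core cut can truncate late Stage 2 patients as well. This cuts both ways: it weakens the contrast, but adds a second route by which power can fall below 81%. Stage 1 patients enroll first, so they have the Stage 2 period in which a late response could still be recorded, and their mismatch remains.

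A reader might also infer that a false stop would end the development program. Neither document says so.

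**Conclusion.** The point holds as a gap in specification. The plan fixes neither when the futility count is taken nor the period over which response is counted, so 81% is the best case rather than the property of the plan as written.

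Under the assumption that 60–80% of eventual responses are visible in the 3 to 5 newest Stage 1 patients, power is about 74–80% (a loss of roughly 1.5 to 7 points) and the false-stop probability about 9–17% instead of 7.1%. If all 9 were affected, power would be 62–75%. The visibility shares and the number of immature patients are assumptions, and the true loss could be close to zero if the look is taken late. Type I error is not inflated; the risk is only that an active drug is stopped. The stated 3.7% and 81% are arithmetically correct for complete data, and the 9/19 design and its bounds need no change.

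**What to change.** In Protocol 8.3.2 and SAP 3.4:

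1. Keep the early go as soon as 2 responses are seen.
2. Allow the futility stop at 0 or 1 responses only when every Stage 1 patient without a response has progressed, stopped treatment, or completed a fixed response window that is the same for all nine (for example through the Cycle 4 MRI, inside the existing Cycle 12 limit).
3. Apply the same window or follow-up rule to the final count of 19, and name the data cut that carries the primary test. A window on Stage 1 alone leaves the two counts different: if 90% of responses in all nine were visible by its end, power would be 78.8%.
4. State that the 14% and 40% refer to response within that window, and choose it with that in mind. If the eventual rate is 40% but a common window misses 10% of responses in both stages, the rate being tested is 0.9 × 40% = 36% and power is 70.7%.

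If the sponsor prefers not to fix the timing, restate 81% as an upper bound in Protocol 8.3.3.2 and SAP 3.3.3.

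Cost: wording in two documents, with no added patients or scans. A futility decision may come about one 8-week scan interval later when stable patients are still on drug, and the final test may have to wait for the last patients to complete the window.

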1.5.2.2.2 Rationale for patient selection in Phase 2a (Simon's two-stage design)

The selection of patients for the Phase 2a study based on EB1 expression in GBM tissue is supported by the following considerations:

- Results of retrospective GBM tissue micro array (TMA) analyses:
 - o TMA from the University of Bern (n=248 patients): This TMA included up to 12 tissue spots per patient (up to 4 tissue spots each from the tumor center, the tumor infiltration front and from normal brain tissue). EB1-positivity on a patient level was defined if EB1 staining was seen in at least 75% of tumor spots from the tumor center and this resulted in a EB1-positive rate of 4%.
 - TMA from the Institute of Cancer Research in the UK (n=354 patients): This TMA included a single GBM tissue spot per patient, and showed an EB1-positive rate of 2%.

The determined prevalence of EB1-positive GBM in a range of 2–4% is considered sufficient for a biomarker driven enrollment strategy.

- Pre-existing non-clinical data supporting EB1 as a response-predictive biomarker for BAL101553 in GBM in mouse models (see Section 1.3.4.1).
- The need for gaining a better understanding of the molecular underpinnings in exceptional responders has recently been highlighted by a dedicated initiative of the US National Cancer Institute (Exceptional Responders Initiative; NCI 2020), and the

Phase 2a portion of this study is designed to assess the utility of EB1 as a response-predictive biomarker for GBM patients in this context.

[figure not shown]
A tissue screening program using IHC and adhering to local standards in selected countries will be established to support the identification of potential patients.

Assuming a prevalence of EB1-positive GBM of 2-4%, screening of GBM tissues from 25-50 GBM patients is required to identify one EB1-positive case.

EB1-tissue staining using IHC has been performed to date at the University of Basel in a retrospective manner using a Ventana discovery platform. For the Phase 2a portion of this study, a dedicated Clinical Trial Assay is being developed on a platform for clinical use in cooperation with an experienced clinical research organization. This Clinical Trial Assay is expected to be available in June 2020. Details of the EB1-tissue staining methodology are provided in Appendix 4, and will be specified in a dedicated laboratory manual.

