Blood samples for PK analysis will be collected at serial time-points, as described in Section 5.7.1. 24-h urine sampling will be performed in solid-tumor patients during the Phase 1 portion of the trial for analysis of drug and drug metabolite excretion (see Section 5.7.2). Urine PK samples will not be taken from GBM/high-grade glioma patients.

Blood samples for biomarker analysis will be obtained on Day 1 of Cycle 1 as described in Section 5.8.1.

5.3.2.2 Day 8, Day 15, Day 22 and Day 28 of Cycle 1 and Cycle 2

Patients will return to the clinic and assessments will be performed in accordance with Table 8, or Table 9 for patients in the Phase 2a portion of the study. Day 28 assessments of a given cycle may be performed on Day 29 of that cycle, i.e., pre-dose on Day 1 of the subsequent cycle.

On the day of drug administration, all patients must have fasted for at least 4 h (see Section 3.1.4 for more details).

Vital signs will be performed pre-dose and post-dose as described in Section 5.5.4; ECG will be performed pre-dose and post-dose as described in Section 5.5.5.

BP measurements should be obtained pre-dose and post-dose, as described in Section 5.5.4 and Table 10.

Laboratory safety tests (hematology, biochemistry and cardiac troponin) will be assessed as described in Section 5.5.7.

Blood samples for pharmacokinetic (PK) analysis will be collected pre-dose on Day 8, Day 15 and Day 22 of Cycles 1 (both Phases) and 2 (Phase 1), as described in Section 5.7.1.

Blood samples for biomarker analysis in Phase 1 will be obtained pre-dose on Day 8, Day 15 and Day 22 of Cycle 1; and Day 22 Cycle 2; as described in Section 5.8.1.1.

In Phase 1, tumor biopsies will be obtained on Day 22 of Cycle 1 and/ Cycle 2, if easily accessible and deemed safe for the patient by the Investigator, and if the patient is willing to undergo biopsy (see Section 5.8.1.2).

Patients with measurable tumors will undergo radiological assessment of the tumor between Days 15 and 28 of Cycle 2. Efficacy assessments for patients with non-measurable ovarian or prostate cancer will be performed between Days 22 and 28 of all cycles. The assessment of cancer and the selection and reporting of radiological marker lesions or other assessment endpoints (CA-125 or PSA) are described in Section 5.6.

If efficacy evaluations on Day 28 of Cycle 2 demonstrate absence of disease progression, patients may be eligible to continue treatment with BAL101553.

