5.6 Efficacy assessments

At Screening, patients with advanced or recurrent solid tumors must have measurable disease (according to RECIST criteria v1.1), or non-measurable disease that can be followed by an acceptable tumor marker (CA-125 or PSA), prior to initiation of study treatment.

Patients with recurrent or progressive glioblastoma or high-grade glioma must be evaluated according to RANO criteria.

All radiological tests that demonstrated tumor at baseline (i.e., at Screening, or within 35 days prior to starting study drug for patients with advanced or recurrent solid tumors or within 15 days prior to starting study drug in patients with recurrent or progressive glioblastoma or high-grade glioma) must be repeated within 1 (Phase 1) or 2 (Phase 2a) weeks of completion of every even numbered cycle prior to the next administration of BAL101553. From Cycle 6 onwards, the interval between CT/MRI scans may be extended from 8 weeks to 12 weeks. Each lesion measured at baseline is to be measured throughout the study by the same method of assessment and the same technique (e.g., consistent use of CT with same anatomic coverage, contrast administration (unless medically contraindicated), slice thickness, and reconstruction interval at all time points) in order to allow for consistent assessments and comparisons. To determine complete response or partial response the required criteria must be present for at least 4 weeks.

Patients with objective response or stable disease will be permitted to continue to receive additional cycles of BAL101553 until disease progression or unacceptable toxicity. No patients are permitted to start subsequent cycles if unequivocal progression is observed, concerning mixed response see Section 4.4.

At study treatment completion (End of Study visit), radiology efficacy assessments must be repeated if these have not been performed within 35 days prior to this day. Assessment of CA-125 or PSA in patients with non-measurable ovarian or prostate cancer must be repeated if these have not been performed within 14 days prior to this day.

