8.3.1.4 Pharmacokinetic analysis population

The PK analysis set includes all patients who received at least one dose of study drug and had at least one post-baseline pharmacokinetic assessment.

8.3.1.5 Efficacy-evaluable population (Phase 2a expansion portion of the study, Simon's two-stage design)

The efficacy evaluable population (EEP) is the subset of the FAP who had at least one postbaseline RANO assessment after having received at least 6 weeks of study treatment.

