4.5 Pharmacokinetic analysis population(PK)

The PK analysis set includes all patients who received at least one dose of study drug and had at least one post-baseline PK assessment.

4.6 Efficacy-evaluable population (Phase 2a expansion portion of the study, Simon's two-stage design)

The efficacy evaluable population (EEP) is the subset of the FAP who had at least one post baseline RANO assessment after having received at least 6 weeks of study treatment.

For objective response rate and stage transition, the analysis will be based on patients with measurable disease at baseline in the EEP.

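### The optional futility termination at enrollment of the last Stage 1 patient rests on at most 8 evaluable patients, and the stated 81% power does not cover its use

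*Protocol*

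**What the plan says.** The sample-size sections (Protocol 8.3.3.2, SAP 3.3.3) contain one futility rule: "If there are 1 or fewer responses in these 9 patients, the study will be stopped". Otherwise 10 more evaluable patients are accrued, and the null hypothesis is rejected at 6 or more responses in 19. The SAP adds: "This design yields a type I error rate of 3.7% and power of 81% when the true response rate is 40" percent.

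The efficacy-evaluable population (Protocol 8.3.1.5) is the part of the full analysis population "who had at least one postbaseline RANO assessment after having received at least 6 weeks of study treatment". SAP 4.6 applies it to the interim decision: "For objective response rate and stage transition, the analysis will be based on patients with measurable disease at baseline in the EEP". On timing, Protocol 5.3.2.2 says: "Patients with measurable tumors will undergo radiological assessment of the tumor between Days 15 and 28 of Cycle 2". Protocol 5.6 adds: "To determine complete response or partial response the required criteria must be present for at least 4 weeks".

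Protocol 8.3.2 and SAP 3.4 time the interim analysis for when the Stage 1 patients have had that assessment. In identical wording, both then add an earlier decision point. If the required number of responses (2, from Protocol 1.5.2.2.1) is not there at "enrollment of the last patient in Stage 1, enrollment may be suspended, or the cohort may be terminated due to apparent futility". Both options are permissive. The next sentence allows earlier transition to Stage 2 once the required responses have been reached.

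**The concern.** The two provisions look at different numbers of patients. The sample-size rule decides on 9 evaluable patients. The added option applies when the ninth has only just been enrolled, at least 6 weeks before that patient can be evaluable. It gives no minimum number of evaluable patients, no criterion beyond the response count, and no operating characteristics.

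At 0 responses in 8 the two agree, because 2 in 9 can no longer be reached. At 1 in 8 they can disagree: the ninth patient may still respond, and the written option allows the cohort to be ended anyway. What is at stake is power in a population that is slow to find, since "screening of GBM tissues from 25-50 GBM patients is required to identify one EB1-positive case". The Surgical cohort also depends on passing Stage 1.

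**Working it through.** **Inputs.** Null rate p0 = 0.14, alternative p1 = 0.40, n1 = 9, continue if at least 2 respond, n = 19, reject at 6 or more (Protocol 8.3.3.2, SAP 3.3.3). The number of Stage 1 patients still unassessed when the last one is enrolled is k, so m = 9 − k are evaluable. The documents fix only that k is at least 1.

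**1. The plan's own figures.** Exact binomial:

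P(reject) = Σ over x = 2 to 9 of P(Bin(9, p) = x) × P(Bin(10, p) ≥ 6 − x)

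- p = 0.14: 0.0371, against the stated 3.7%.
- p = 0.40: 0.8132, against the stated 81%.

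Both reproduce, with no futility look other than the one at 9 patients.

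**2. Why at most 8.** The first on-treatment scan falls on Cycle 2 Days 15 to 28, which is study day 28 + 15 = 43 to 28 + 28 = 56. A patient just enrolled has no such scan, so k ≥ 1.

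**3. One patient unassessed (k = 1), p = 0.40.**

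- P(0 in 8) = 0.0168. A stop here agrees with the 9-patient rule.
- P(1 in 8) = 0.0896. The ninth patient responds with probability 0.40, so P(1 in 8, then a response) = 0.0896 × 0.40 = 0.0358. Here the 9-patient rule continues.
- P(stop) is 0.0705 under the 9-patient rule. If the option is always used it is 0.0168 + 0.0896 = 0.1064.
- After 2 in 9, Stage 2 needs at least 4 responses in 10: P(Bin(10, 0.40) ≥ 4) = 0.618.
- Power lost = 0.0358 × 0.618 = 0.0221, so power = 0.8132 − 0.0221 = 0.7911.
- If used half the time: 0.8132 − 0.0111 = 0.8022 (to rounding). If never used: 0.8132.

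**4. The same case at p = 0.14.** P(0 in 8) + P(1 in 8) = 0.2992 + 0.3897 = 0.6889. Of this, 0.3897 × 0.14 = 0.0546 would have continued. So 0.0546 / 0.6889 = 7.9% of early stops disagree with the full rule and 92.1% agree. At p = 0.40 the disagreement is 0.0358 / 0.1064 = 33.7%.

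**5. More patients unassessed, option always used at fewer than 2 responses.**

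| Unassessed k | Evaluable m | P(stop), p = 0.40 | Power | Type I error |
|---|---|---|---|---|
| 0 (plan) | 9 | 7.1% | 81.3% | 3.7% |
| 1 | 8 | 10.6% | 79.1% | 3.5% |
| 2 | 7 | 15.9% | 75.4% | 3.2% |
| 3 | 6 | 23.3% | 69.6% | 2.8% |
| 4 | 5 | 33.7% | 61.0% | 2.2% |

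The rows from k = 2 down depend on accrual. Assuming even spacing, the eighth patient is unassessed as well (k at least 2) whenever patients with measurable disease enroll less than about 6 to 8 weeks apart, the time to the first scan.

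**6. Bounded rule.** If an early stop is allowed only when (responses among m) + k ≤ 1, it never contradicts the 9-patient rule. Power stays 81.3% and type I error 3.7% for k = 0 to 4.

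**The case against.** **The option is discretionary and its qualifier can be read narrowly.** A sponsor could suspend at 1 in 8 and terminate only at 0 in 8, which costs no power. That is a fair reading of sensible conduct, and the 79.1% does assume termination at every 1 in 8. But neither document defines apparent futility, and the only stated trigger is that the required responses have not been seen. Termination at 1 in 8 is within the text.

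**The certain effect is small.** With one patient unassessed the loss is 0 to about 2 points, in a 19-patient single-arm study. This stands and limits the severity.

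**The sponsor may terminate at any time anyway (Protocol 9.5).** True, but that is a general right, not a futility option written into the interim-analysis paragraph beside a rule with quoted power.

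**The option has value if the drug is inactive.** At a true 14% rate, 92% of early stops agree with the full rule. The bounded rule keeps the stop at 0 in 8, though not the one at 1 in 8.

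**Stronger readings.** A reader might infer that the 3.7% type I error is no longer controlled. It is: an extra futility stop can only remove rejections. A reader might also take 61% to 75% as the trial's real power. The documents do not support that. They give no accrual rate, and screening 25 to 50 tissues per EB1-positive case suggests slow enrollment, which points toward one unassessed patient. Nor do the documents require termination, and suspending enrollment until the ninth patient is assessed leaves the operating characteristics unchanged.

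**Conclusion.** The point holds as a minor-to-moderate one. Both documents allow, without requiring, a futility termination when at most 8 of the 9 Stage 1 patients can be evaluable, and the 81% power was calculated without it. At a true 40% rate with one patient unassessed, power lies between 79.1% (always used) and 81.3% (never used).

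Losses to 75.4%, 69.6% or 61.0% require 2, 3 or 4 unassessed patients and consistent use of the option; both are assumptions. The 3.7% stands as the maximum type I error. All figures assume independent responses with a common rate, and that the evaluable patients' response status at the early look is the one that would count at the interim analysis.

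**What to change.** In Protocol 8.3.2 and SAP 3.4, keep the option to suspend enrollment and replace the termination half of the sentence with:

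*A Stage 1 futility stop is decided on 9 evaluable patients with measurable disease at baseline (EEP), or earlier only if 2 responses among the 9 can no longer be reached, counting each patient by the response status that would be used at the 9-patient interim analysis (for example, 0 responses in 8 evaluable patients). If a CR or PR awaiting the 4-week requirement of Section 5.6 would change the decision, the decision is held until it has been checked. A suspension does not prevent replacement of a non-evaluable Stage 1 patient under Section 4.5.*

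Earlier transition once 2 responses are reached can stay, because 2 responses already guarantee passing Stage 1.

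Alternatively, keep the option, call it non-binding, and state that 3.7% is the maximum type I error and that power is below 81% if the option is used (79.1% at 8 evaluable when always used).

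The cost of the first version is one paragraph in each document and a possible pause of about 6 to 8 weeks for the last patient's first scan, which the sentence already permits. Add at least 4 weeks if a pending CR or PR is decisive. The pause is longer if the ninth patient proves non-evaluable and must be replaced; Protocol 3.3 assumes about 25% non-evaluability, so this is a realistic possibility.
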